17.7.2 Pharmacokinetics of nicotine in plasma

The following non-compartmental PK parameters will be determined for each IP: AUC_{0-inf} , AUC_{0-last} , $AUC_{0-l.5h}$, C_{max} , T_{max} and $T_{1/2}$. Where possible, both baseline-adjusted and non-adjusted PK parameters will be calculated.

 C_{max} and T_{max} will be derived from the observed nicotine plasma concentration data. AUC_{0-1.5h} and AUC_{0-last} will be calculated using log-linear trapezoidal interpolation. Calculations will be based on the actual sampling times recorded during the study. Concentrations below the lower limit of quantification (LLOQ) occurring before C_{max} will be treated as zero. Concentrations below LLOQ occurring after C_{max} will be omitted from the analysis. All baseline-adjusted PK parameters will be corrected for nicotine plasma concentrations at baseline (preadministration).

AUC_{0-inf} will be calculated as described in Section 17.4 above.

The equivalence in $AUC_{0\text{-inf}}$ and C_{max} between the unflavored NP 6 mg and each flavored NP 6 mg will be assessed using a mixed model with the natural log of AUC_{inf} as the dependent variable, treatment as a fixed effect and subject as a random effect. The improved Kenward-Roger's approximation for degrees of freedom will be used. The estimated LSMeans difference between unflavored NP 6 mg and flavored NP 6 mg will be back transformed into the original scale to present the ratio of geometric LSMeans as well as the corresponding 90 % confidence interval. If the 90% confidence interval of this ratio falls within the range 0.8-1.25, the IPs will be considered equivalent. The model will be estimated for both non-adjusted and baseline adjusted $AUC_{0\text{-inf}}$.

17.7.3 Pharmacodynamic effects

The analyses of pulse rate as a measure of the PD effect of nicotine will be further described in the SAP. Data will be presented as summary tables of descriptive statistics and plots of pulse rates over time for each IP.

The subjective parameters "craving", "satisfaction", "product-liking" and "intent to use again", measured by VAS, will be summarized for each IP using descriptive statistics as a total score during the IP administration phase. The relative and absolute change from baseline will also be calculated for the subjective parameter "craving" for each IP.

To determine the maximum PD effect attributable to the IP, the highest recorded increase (E_{max}) as well as time to first instance of E_{max} will be calculated for the pulse rates as well as for the subjective parameter "craving". For the subjective parameter "satisfaction", which does not have a baseline, the maximum value will be recorded as E_{max} along with time to E_{max} .

CONFIDENTIAL 59(64)

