3 LIST OF ABBREVIATIONS AND DEFINITION OF TERMS

Abbreviation	Explanation						
ADL	Activities of daily living						
AE	Adverse event						
AUC	Area under the plasma concentration vs. time curve						
$\mathrm{AUC}_{0\text{-inf}}$	AUC from 0 to infinity						
AUC _{0-last}	AUC from 0 to time of last measurable plasma concentration						
AUC _{0-1.5h}	AUC from time 0 to time 1.5 h						
BMI	Body mass index						
C_{max}	Maximum observed concentration						
CRO	Contract research organization						
CSP	Clinical study protocol						
CSR	Clinical study report						
CTC	Clinical Trial Consultants AB						
CTCAE	Common terminology criteria for adverse events						
CV	Coefficient of variation						
ECG	Electrocardiogram						
eCRF	Electronic case report form						
EDC	Electronic data capture						
EEA	European Economic Area						
E_{max}	Highest recorded change from baseline						
EU	European Union						
FDA	United States Food and Drug Administration						
GCP	Good clinical practice						
GDPR	General data protection regulation						
HIV	Human immunodeficiency virus						
HR	Heart rate						
ICF	Informed consent form						
ICH	International Council for Harmonisation of Technical Requirements for Pharmaceuticals for Human Use						
IEC	Independent ethics committee						
IP	Investigational product						
ISF	Investigator site file						
LLOQ	Lower limit of quantification						

CONFIDENTIAL 13(64)

Abbreviation Explanation ADL Activities of daily living **LSMeans** Least-squares means **MCQ** Multiple-choice question NP Nicotine pouch **NRT** Nicotine replacement therapies PD Pharmacodynamics PΙ **Principal Investigator** PK Pharmacokinetics **PKAS** PK analysis set QC Quality control **RBM** Risk based monitoring SAE Serious adverse event **SAP** Statistical analysis plan **SAS** Statistical analysis software SD Standard deviation **SDV** Source data verification SOC System organ class **SOP** Standard operating procedures Terminal elimination half-life $T_{1/2}$ T_{max} Time of occurrence of C_{max} **TMF** Trial master file US United States (of America) VAS Visual Analogue Scale **WHO** World Health Organization

CONFIDENTIAL 14(64)

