7.2.1 Secondary endpoints

- 1. Extraction from pouches: The difference in *in vivo* extracted amount (mg/unit) and extracted fraction (%) of nicotine between the unflavored NP 3 mg and 6 mg products and the comparator product, Longhorn Natural 18 mg.
- 2. PK of nicotine in plasma: The difference between the unflavored NP 3 mg and 6 mg products and the comparator product, Longhorn Natural 18 mg, in the non-adjusted and baseline-adjusted PK parameters based on plasma concentrations of nicotine:
 - o AUC_{0-inf},
 - \circ maximum observed concentration (C_{max}),
 - o time of occurrence of C_{max} (T_{max}),
 - \circ AUC from 0 to 1.5 hours (AUC_{0-1.5h}),
 - o AUC from 0 to time of last measurable time point (AUC_{0-last}),

CONFIDENTIAL 22(64)

- \circ terminal elimination half-life ($T_{1/2}$)
- 3a. PD (pulse rate): The difference between the unflavored NP 3 mg and 6 mg products and the comparator product, Longhorn Natural 18 mg, for the highest recorded increase (E_{max}) in pulse rate from baseline, measured using a pulse oximeter after IP administration.
- 3b. PD parameters: The difference between the unflavored NP 3 mg and 6 mg products and the comparator product, Longhorn Natural 18 mg, for the highest recorded value (E_{max}) in the subjective parameters "craving" and "satisfaction", measured using a 100 mm visual analogue scale (VAS) after IP administration.
- 3c. PD (subjective outcome parameters): The difference between the unflavored NP 3 mg and 6 mg products and the comparator product, Longhorn Natural 18 mg, for the subjective parameters "product-liking" and "intent to use again", measured using a 100 mm VAS 30 minutes after IP administration.
- 4. Extraction from pouches: The difference in *in vivo* extracted amount (mg/unit) and extracted fraction (%) of nicotine between the unflavored NP 6 mg and the flavored NP 6 mg products.
- 5a. \underline{PK} of nicotine in plasma: The equivalence between the unflavored NP 6 mg and flavored NP 6 mg products in the non-adjusted and baseline-adjusted PK parameters \underline{AUC}_{0-inf} and \underline{C}_{max} based on plasma concentrations of nicotine.
- 5b. PK of nicotine in plasma: The difference between the unflavored NP 6 mg and flavored NP 6 mg products in the non-adjusted and baseline-adjusted PK parameters T_{max} , $AUC_{0-1.5h}$, AUC_{0-last} , and $T_{1/2}$.

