9.6.1 General restrictions

- 1. Contraception requirements: Subjects of child-bearing potential are expected to use contraceptive methods in accordance with inclusion criterion #6 or practice abstinence from heterosexual intercourse (only allowed when this is the preferred and usual lifestyle of the subject) during the clinical study.
- 2. Tobacco/nicotine products: Subjects shall abstain from any self-administered oral tobacco/nicotine products as well as smoking (cigarettes and e-cigarettes) for at least 12 hours prior to treatment visits and during each treatment visit (Visits 2-12).
- 3. Mouth related procedures: Subjects shall abstain from eating, drinking, or conducting any other mouth related procedure (*e.g.*, tooth brushing) for 30 minutes prior to IP administration, during IP use, and for 30 minutes after IP removal (Visits 2-12).
- 4. Drugs of abuse: Subjects shall abstain from any drugs of abuse during the study, *i.e.*, from screening (Visit 1) to the last treatment visit (Visits 12).
- 5. Alcohol: Subjects shall abstain from alcohol for at least 12 hours prior to each treatment visit (Visits 2-12).
- 6. Blood donation: The subjects must not donate blood or plasma within 1 month of screening until 3 months after the last treatment visit (Visits 12).
- 7. Participation in other clinical studies: The subjects are not allowed to participate in any other clinical study from the screening visit (Visit 1) until the last treatment visit (Visit 12).

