11.4.2.2 Subjective parameters

Subjective parameters ("craving", "satisfaction", "product-liking", and "intent to use again") will be rated using VAS, anchored with "not at all" to "extremely", or "very likely" for the "intent to use again" parameter.

The "craving" parameter will be assessed with the question "Right now, how strong is your urge to snus?" at the same pre-defined time points as the pulse-rate assessments: -10 min prior to IP administration, and 5 min, 10 min, 15 min, 20 min, 30 min, 40 min, 60 min, 1 h:30 min, 2 h, 4 h, and 6 h post-administration.

The "satisfaction" parameter will be assessed with the question "Right now, is the product satisfying?" at the pre-defined time points: 5 min, 10 min, 15 min, 20 min, 30 min, 40 min, 60 min, 1 h:30 min, 2 h, 4 h, and 6 h post-administration.

In addition, "product-liking" and "intent to use again" parameters will be assessed at 30 minutes post-administration with the questions "How much did you like the product?" and "How likely are you to use this product again in the future?", respectively.

Time points for each of the VAS questions are outlined in Table 8.1-2, and allowed deviations from actual time are outlined in Table 11.1-1.

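### The craving part of secondary endpoints 3b and 6b is defined in the wrong direction, and in three inconsistent ways

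*Protocol*

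**What the plan says.** Emax for craving is worded in three ways in the Protocol.

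- **Highest value.** Endpoint 3b in section 7.2.1 compares products "for the highest recorded value (E_{max}) in the subjective parameters" craving and satisfaction. Endpoint 6b and the synopsis use the same wording.
- **Highest increase.** Section 17.7.3 states its purpose and rule together: "To determine the maximum PD effect attributable to the IP, the highest recorded increase". The sentence covers pulse rate and craving, and it adds the time to the first Emax.
- **Highest change.** Section 3 expands Emax as "Highest recorded change from baseline", with no direction.

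The craving question in section 11.4.2.2 is "Right now, how strong is your urge to snus". The subjective items "will be rated using VAS, anchored with 'not at all' to 'extremely" (the upper anchor differs only for intent to use again). Craving is rated once before administration and at 11 times from 5 min to 6 h afterwards.

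Section 17.7.3 plans two other craving summaries: absolute and relative change from baseline, and a descriptive total score over the administration phase. For satisfaction, which has no baseline, it takes the maximum value.

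**The concern.** For pulse rate the effect of nicotine is a rise, and for satisfaction a good product scores high. A maximum suits both. Craving runs the other way. Section 6.1, writing about smokers, links a product's nicotine delivery to its ability to reduce craving, and the same direction is expected in these subjects. A rule that takes the maximum therefore reports the moment of least relief under the name of the product's greatest effect.

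Subjects arrive after at least 12 hours without nicotine and take none of their own during the visit (section 9.6.1). The pouch is removed at 30 min, but rating continues to 6 h. The highest score is thus open to being set by the return of craving long after use.

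At stake is the named craving statistic for ten product contrasts: two against the comparator (3b) and eight flavored against unflavored (6b). Section 6.1 says the results are meant for a premarket application to the FDA, which asks for data on nicotine effects.

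**Working it through.** The Protocol gives no craving figures, so there is no planned number to reproduce. The check compares the definitions and then illustrates them.

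**Step 1: the definitions as formulas.** Let B be the pre-administration score and Y(t) the 11 later scores.

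- Endpoints 3b and 6b: max Y(t).
- Section 17.7.3: max Y(t) − B.
- Relief: B − min Y(t).

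Within one visit the first two pick the same time point and differ only by B. Neither uses the lowest score. Section 3 equals the second formula if the change is read with its sign; it could admit a decrease only if read as a magnitude.

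**Step 2: a hand example (assumed values).** Baseline is 70 mm. The lowest score is 20 mm with one product and 45 mm with another, and both return to 75 mm at 6 h.

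- Highest value: 75 mm for both.
- Highest increase: 75 − 70 = +5 mm for both.
- Maximum decrease: 70 − 20 = 50 mm against 70 − 45 = 25 mm, a difference of 25 mm.

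The tie follows from the assumed common 6 h score. The example shows that the planned rules can miss a 25 mm difference, not that they will.

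**Step 3: a simulation (all inputs assumed).** Times are the Protocol's 11 post-administration times. Baseline has mean 60 mm and SD 18 mm, and each reading has noise with SD 8 mm. Relief rises linearly to its peak at 30 min and then fades with a 90 min time constant. A late rise above baseline grows linearly to 0, 10 or 20 mm at 6 h. Scores are held within 0 to 100 mm, with 20,000 subjects per setting. Entries are means in mm.

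| Late rise | Statistic | Relief 40 | Relief 25 | Relief 15 | Relief 0 | 40 minus 0 |
|---|---|---|---|---|---|---|
| 0 | Highest increase | 3.6 | 5.5 | 7.3 | 12.3 | −8.7 |
| 0 | Highest value | 63.2 | 65.2 | 67.2 | 72.1 | −8.9 |
| 0 | Maximum decrease | 41.2 | 29.5 | 21.8 | 12.5 | +28.7 |
| 10 | Highest increase | 10.8 | 11.9 | 12.9 | 15.6 | −4.8 |
| 10 | Highest value | 70.7 | 71.8 | 72.7 | 75.3 | −4.6 |
| 10 | Maximum decrease | 40.7 | 28.5 | 20.7 | 10.9 | +29.8 |
| 20 | Highest increase | 19.0 | 19.5 | 19.9 | 21.2 | −2.2 |
| 20 | Highest value | 78.8 | 79.7 | 79.7 | 81.0 | −2.2 |
| 20 | Maximum decrease | 39.7 | 27.6 | 19.7 | 9.7 | +30.0 |

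Both planned rules shrink a true 40 mm difference to between 2.2 and 8.9 mm and reverse its sign. The maximum decrease keeps the order. It is not free of noise: a product with no relief still shows 9.7 to 12.5 mm, because an extreme of 11 noisy readings is taken.

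**Step 4: time to Emax.** With 40 mm of relief, 74%, 93% and 98% of the highest-increase times fall at 4 or 6 h for late rises of 0, 10 and 20 mm. The median time of the maximum decrease is 30 min for every simulated product that gives relief.

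**The case against.** The best reply is that the Protocol does not rely on Emax alone. Section 17.7.3 plans change from baseline and a total score for craving, and both can show relief in the right direction. Satisfaction, the other half of 3b and 6b, is defined correctly. Section 17.7.3 sets no test, margin or success criterion for craving Emax. The lowest score and its time can be derived from the planned ratings at any stage. Section 3 is neutral on direction, and the purpose stated in 17.7.3 suggests pulse-rate wording carried over to craving rather than a decision to measure worst craving.

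All of this stands and limits the point. It does not rescue the definition. The other craving summaries are not the named endpoint, and the time of greatest relief is defined nowhere. Nor is this detail left to the SAP. The Protocol states the rule, so a SAP that follows it repeats the error and one that corrects it departs from the stated endpoint.

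A reader might infer more than the documents support:

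- That 3b and 6b cannot measure any product effect. Satisfaction is sound, and even craving Emax keeps a weak, reversed signal.
- That product differences in craving will be hidden. The other planned summaries can show them.
- That the highest craving will be the 6 h reading, or a 5 min reading taken before any uptake. The Protocol gives no craving or onset data, and it schedules a blood sample at 5 min.

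**Conclusion.** The point holds for the craving component of endpoints 3b and 6b. The value and increase rules point the wrong way on an urge scale, and the three wordings contradict one another whichever direction is intended. As written, craving Emax and time to Emax describe the worst post-administration craving and reflect relief only weakly and in reverse.

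The direction follows from the Protocol's own item, anchors and background, without assumptions. The size rests on the assumed inputs of the simulation, and real craving curves could give a stronger or weaker reversed signal.

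This should be fixed, but it is not critical to the trial's main conclusion. The primary endpoint is baseline-adjusted AUC, the sample size rests on PK equivalence, and neither uses craving.

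**What to change.** In the synopsis, section 7.2.1 (3b and 6b) and section 17.7.3, define craving Emax as the maximum decrease from the pre-administration score, that is, baseline minus the lowest post-administration score. Define time to Emax as the time of the first occurrence of that lowest score. Keep the highest increase for pulse rate and the highest value for satisfaction, and state the three definitions separately. Change the entry in section 3 so that it points to these parameter-specific definitions; its present wording also does not fit satisfaction, which has no baseline.

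The cost is a wording amendment to the Protocol and matching text in the SAP before database lock. No new data, visits or subjects are needed.

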17.7.4 Adverse events

An overview of all AEs, including SAEs, intensity, and deaths will be presented by IP. The incidence of AEs and SAEs will be summarized by SOC and PT by IP.

All AE data will be listed by subject number and include the verbatim term entered by the Investigator.

17.8 Analysis of exploratory objectives

17.8.1 Exploratory subjective parameter

The subjective parameter "product-liking" vs. the subjects' usual snus/nicotine product of choice, measured through MCQ, will be summarized for each IP using descriptive statistics.

17.8.2 Extraction normalized AUC_{0-inf} and C_{max}

Nicotine extraction-normalized PK parameters $AUC_{0\text{-inf}}$ and C_{max} (with and without baseline-adjustment) will be determined for the unflavored NP 3 mg and 6 mg products and the comparator product, Longhorn Natural 18 mg as well as for the unflavored NP 6 mg and flavored NP 6 mg products. The difference in $AUC_{0\text{-inf}}$ and C_{max} and the extracted amount and fraction of nicotine between the flavored NP 6 mg product with the highest concentration and Longhorn Natural 18 mg will be analyzed. Extraction-normalized $AUC_{0\text{-inf}}$ and C_{max} data will be presented for each IP using summary statistics.

CONFIDENTIAL 60(64)

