- 1. The difference in "product-liking" vs. the subjects' usual oral tobacco/nicotine product of choice between the unflavored NP 3 mg and 6 mg products and the comparator product, Longhorn Natural 18 mg, measured on a 3-point scale using a multiple-choice question (MCQ) 30 min after IP administration.
- 2. The difference in nicotine extraction normalized AUC_{0-inf} and C_{max} between the unflavored NP 3 mg and 6 mg products and the comparator product, Longhorn Natural 18 mg.
- 3. The difference in "product-liking" *vs.* the subjects' usual oral tobacco/nicotine product of choice between the unflavored NP 6 mg and flavored NP 6 mg products, measured on a 3-point scale using a MCQ 30 minutes after IP administration.
- 4. The difference in nicotine extraction normalized AUC_{0-inf} and C_{max} between the unflavored NP 6 mg and flavored NP 6 mg products.
- 5. The difference in the PK parameters AUC_{0-inf} and C_{max} and the extracted amount and fraction of nicotine between the flavored NP 6 mg product with the highest concentrations and the comparator product, Longhorn Natural 18 mg.

The results of the exploratory objectives may not be reported in the clinical study report (CSR).

Number of subjects planned

Approximately 66 subjects are planned to be screened to achieve 36 randomized subjects and at least 32 evaluable subjects, *i.e.*, subjects who have received all 11 IPs.

An effort will be made to randomize at least 14 female subjects (approximately 40%).

Diagnosis and main eligibility criteria

Healthy male or female subjects aged ≥ 21 to ≤ 60 years who have used oral tobacco/nicotine pouch products for ≥ 1 year, with a minimum daily consumption of 5 or more pouches, who are willing and able to use both tobacco-based moist snuff and NPs with high nicotine content, may be considered to be eligible for participation in the study. All subjects must be willing to comply with study procedures and give written informed consent. Female subjects of child-bearing potential must practice abstinence from heterosexual intercourse (only allowed when this is the preferred and usual lifestyle of the subject) or must agree to use a highly effective method of contraception with a failure rate of <1% to prevent pregnancy for the duration of the study.

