7.3.1 Exploratory endpoints

- 1. The difference in "product-liking" *vs.* the subjects' usual oral tobacco/nicotine product of choice between the unflavored NP 3 mg and 6 mg products and the comparator product, Longhorn Natural 18 mg, measured on a 3-point scale using a multiple-choice question (MCQ) 30 minutes after IP administration.
- 2. The difference in nicotine extraction normalized AUC_{0-inf} and C_{max} between the unflavored NP 3 mg and 6 mg products and the comparator product, Longhorn Natural 18 mg.
- 3. The difference in "product-liking" *vs.* the subjects' usual oral tobacco/nicotine product of choice between the unflavored NP 6 mg and flavored NP 6 mg products, measured on a 3-point scale using a MCQ 30 minutes after IP administration.
- 4. The difference in nicotine extraction normalized AUC_{0-inf} and C_{max} between the unflavored NP 6 mg and flavored NP 6 mg products.
- 5. The difference in the PK parameters AUC_{0-inf} and C_{max} and the extracted amount and fraction of nicotine between the flavored NP 6 mg product with the highest concentrations and the comparator product, Longhorn Natural 18 mg.

CONFIDENTIAL 24(64)

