8.1 Overall study design and schedule of events

This is a multi-center, open-label, randomized, 11-way cross-over, single dose administration study, designed to assess nicotine exposure from new format NP products. The IPs include 2 unflavored products (3 mg and 6 mg) and 8 flavored products (Flavor A-H 6 mg). The comparator product is Longhorn Natural 18 mg.

The study will include 36 randomized subjects with the aim of achieving 32 evaluable subjects. The subjects are healthy male or female oral tobacco/nicotine pouch users aged 21 to 60 years, inclusive, who have used oral tobacco/nicotine products for ≥1 year, with a minimum daily consumption of 5 or more pouches. An effort will be made to randomize at least 14 female subjects (approximately 40%). Each subject will participate in the study for approximately 5 weeks, not including the preceding 4-week screening period.

An overview of the study design is shown in Figure 8.1-1.

Figure 8.1-1 Overview of the study design

Subjects will report to the study sites for a screening visit (Visit 1) followed by 11 treatment visits (Visits 2-12) on separate days. Screening will take place within 4 weeks prior to Visit 2 and will include an eligibility check, including evaluations of smoking and oral tobacco/nicotine use, a brief physical examination, serology tests, electrocardiogram (ECG) and collection of medical history, vital signs (pulse rate and blood pressure), height, weight, and body mass index (BMI) and a product familiarization session. For details, refer to Table 8.1-1.

At the end of the screening visit, the subjects will complete a product familiarization session. During this session, they will be provided with the comparator product, Longhorn 18 mg nicotine, to ensure the acceptability of the product. The subjects will use the product in the same way they would normally use a snus or NP product (*i.e.*, placing it under the upper lip). The duration of product use will be a minimum of 20 minutes, starting from the moment the subject places it in their mouth until they remove it. Subjects who successfully complete this familiarization session, tolerating the product without significant unexpected adverse effects, will be allowed to continue in the study.

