17.2 Determination of sample size

About 66 subjects will be screened to achieve 36 randomized subjects and 32 fully evaluable subjects. A fully evaluable subject is defined as a subject who has received all 11 IPs and who has completed all study visits. An effort will be made to randomize at least 14 female subjects (approximately 40 %).

The sample size has been calculated considering the secondary endpoint: to show equivalence between the unflavored NP 6 mg and flavored NP 6 mg products. A lower number of subjects will be needed for the primary endpoint. Using a CV of 29 %, based on previous studies, a power of 80 %, a significance level of 10 %, lower and upper equivalence bounds of 0.8 and 1.25, and a null ratio of 1, 32 evaluable subjects will be needed. Assuming a dropout rate of 10 %, a total of 36 subjects will be randomized.

CONFIDENTIAL 56(64)

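### Exploratory endpoint 5 gives a ratio to Longhorn only for whichever flavor turns out highest; report the ratio with a 90 % CI for all eight flavors instead

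*Protocol*

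**What the plan says.** The study tests "8 flavored products (Flavor A-H 6 mg"), unflavored 3 mg and 6 mg products, and Longhorn Natural 18 mg as comparator (Protocol, section 8.1). All subjects are meant to receive all eleven products.

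The PK comparisons fall into three layers:

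- **Primary (17.6.1):** unflavored 6 mg against Longhorn on baseline-adjusted AUC0-inf, with the upper 90 % limit to lie below 1.25.
- **Secondary (17.7.2):** each flavored 6 mg product against unflavored 6 mg, on AUC0-inf and Cmax, with equivalence limits 0.8 to 1.25.
- **Exploratory endpoint 5 (synopsis, 7.3.1, 17.8.2):** AUC0-inf, Cmax and extraction, "between the flavored NP 6 mg product with the highest concentrations and the comparator product" (7.3.1). Section 17.8.2 plans that the difference "between the flavored NP 6 mg product with the highest concentration and Longhorn Natural 18 mg will be analyzed".

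The last is the only planned PK contrast of any flavored product with Longhorn. Section 7.3.1 refers to the highest concentrations and 17.8.2 to the highest concentration. Neither says whether Cmax, AUC0-inf or something else decides, or whether the deciding value is baseline-adjusted.

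Descriptively, section 17.4 summarizes PK for every product, and 17.7.1 gives mean extracted amount and fraction for all flavored products and for Longhorn. Section 17.1 rules out any multiplicity adjustment. On reporting, the synopsis says: "The results of the exploratory objectives may not be reported in the clinical study report (CSR").

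**The concern.** Picking the largest of eight observed means and then estimating its ratio from the same data gives an estimate that is too high on average, because the flavor is picked partly for its favorable random error. An ordinary 90 % CI takes no account of the selection. AUC0-inf and Cmax, adjusted or not, may also point to different flavors, so the text does not fix which product is compared.

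Section 6.1 of the protocol describes the eight flavored products as investigated in comparison with Longhorn, and says that some flavors may increase nicotine uptake. With the plan as written, a reader who wants the exposure of a particular flavor relative to the comparator finds no ratio with an interval for seven of them. For the eighth the ratio carries a selection bias.

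**Working it through.** **Inputs.** Section 17.2 states: "Using a CV of 29 %, based on previous studies, a power of 80 %, a significance level of 10" %, with "lower and upper equivalence bounds of 0.8 and 1.25, and a null ratio of 1, 32 evaluable subjects will be needed". It continues: "Assuming a dropout rate of 10 %, a total of 36 subjects will be randomized". There are eight flavored candidates (8.1). The protocol does not say that 29 % is a within-subject CV. That is assumed here, with independent within-subject errors.

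**Reproducing the plan's own figure.** The log-scale SD is √ln(1 + 0.29²) = 0.284. The SE of a log ratio is 0.284 × √(2/n). Two one-sided 5 % tests at a true ratio of 1 reach 80 % power at n = 30 (81.4 %), or at n = 31 if 0.29 is used directly as the log SD. At n = 32 the power is 84.6 %. Dropout: 32/0.9 = 35.6, hence 36. The stated 32 and 36 are consistent with this reading, so the same SD is used below. The protocol gives no figure for the comparison of the highest flavor with Longhorn.

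**Selection bias when all eight flavors are equal.** The SE of one product mean is 0.284/√32 = 0.0502. The expected maximum of eight independent standard normal values is 1.424. The bias on the log scale is 1.424 × 0.0502 = 0.0715, and exp(0.0715) = 1.074. With 36 subjects: 0.284/√36 = 0.0474, 1.424 × 0.0474 = 0.0674, and exp(0.0674) = 1.070.

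**Other configurations** (400,000 simulated trials each; factor by which the ratio of the selected flavor to Longhorn exceeds that flavor's true ratio):

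| True flavor means | n = 32 | n = 36 |
|---|---|---|
| All eight equal | 1.074 | 1.070 |
| One 5 % higher | 1.067 | 1.062 |
| One 10 % higher | 1.044 | 1.038 |
| Evenly spread, −0.1 to +0.1 on the log scale | 1.044 | 1.040 |
| One 25 % higher | 1.001 | 1.001 |

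**Coverage of the unadjusted 90 % CI for the selected flavor, n = 32.**

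- All eight equal: about 78 %.
- One at 1.25 times Longhorn and seven at 1.15: about 83 %.
- One at 1.25 and seven at 1.0: about 90 %.

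**Direction.** The protocol sets no margin for this comparison. If the primary rule (upper limit below 1.25) were borrowed, the chance at n = 32 of wrongly concluding that the selected flavor is below 1.25 would be:

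- 0.05 % with all eight at 1.25;
- 1.4 % with one at 1.25 and seven at 1.15;
- 5.0 % with one at 1.25 and seven at 1.0.

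It does not exceed the nominal 5 %.

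**The case against.** The strongest defense is that this is a sensible worst-case check. If the flavor that looks highest is not above Longhorn, the other seven estimates are lower still, and the upward bias makes that conclusion harder to reach. This stands on the parameter used for selection. It also means that the fix would hardly change a worst-case decision: with near-complete crossover data and a common SE, the flavor with the highest estimate also has the highest upper limit. What the defense does not supply is a usable estimate for any named flavor, or cover on a parameter other than the one that selects, which the protocol leaves open.

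The protocol also asks a different main question about flavors, namely whether they change uptake relative to the unflavored product, and 17.7.2 answers it for each flavor. The endpoint is exploratory, has no margin and supports no primary or secondary conclusion. The selection parameter may be defined in the SAP, which is not at hand. All this limits the weight of the point. But the protocol itself fixes a single data-picked contrast, and its Background frames the comparison with Longhorn more widely.

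Four stronger readings are tempting and not supported:

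- **That the bias could make a flavor look acceptable when it is not.** It runs the other way.
- **That seven flavors are never set beside Longhorn.** Sections 17.4 and 17.7.1 give descriptive PK and extraction for every product, and there is an indirect link through unflavored 6 mg. Only a PK ratio with an interval is missing.
- **That the two margins chain to 1.25 × 1.25 = 1.56 times Longhorn.** This ignores the direct check on the highest flavor. It also needs both true ratios at their limits and both tests to pass. Each then passes about 5 % of the time, so even independent tests would both pass only 0.05 × 0.05 = 0.25 % of the time. The shared unflavored mean makes the two estimates negatively correlated and the joint chance smaller still.
- **That the regulatory application covers every flavor.** Section 6.1 says that the results are intended as a basis for an application, no more.

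On reporting, the synopsis sentence should be read with 15.7.1, which allows exploratory results to be reported separately.

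**Conclusion.** The point holds as a limited one. The only planned PK contrast of a flavored product with Longhorn is for a flavor picked by its own data under an undefined rule, and seven flavors have no ratio to Longhorn with an interval. The picked ratio is overstated by 0 % to about 7 %, with coverage of its 90 % CI falling from about 90 % to about 78 % as the flavors become more alike. These figures rest on 29 % being the within-subject CV, independent errors and 32 evaluable subjects. The upper end applies only if all eight flavors are truly equal. No primary or secondary conclusion is affected, and a finding that the selected flavor is not higher than Longhorn would be conservative. The change is worth making because it is cheap and serves the aim stated in the Background.

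**What to change.** In exploratory endpoint 5 (synopsis and 7.3.1), the matching exploratory objective (synopsis and 7.3) and 17.8.2, replace the single selected contrast with this: for each of the eight flavored 6 mg products, the geometric LSMean ratio to Longhorn Natural 18 mg with its 90 % CI, for baseline-adjusted AUC0-inf and Cmax, from one mixed model that includes all products, together with extracted amount and fraction. Keep the exploratory label, state that the intervals are unadjusted, and report all eight together, wherever the exploratory results are reported. The highest flavor can then be read off each parameter without a selection step, and no selection rule is needed.

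The cost is seven more contrast lines per parameter and the wording change. No subjects, visits or samples are added. The remaining drawback is eight unadjusted intervals per parameter: a reader who singles out the largest afterwards meets the same selection effect, but with the other seven in view.
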